## 7.0 TREATMENT PLAN

### 7.1 **Subject Treatment**

Subjects will be randomized 1:1 to receive low-dose tamoxifen 5 mg or placebo daily for 24 months.

Subjects will be instructed to swallow the capsule whole, with water or another non-alcoholic liquid, preferably the same time each day. They may take the tamoxifen capsules with or without food. If they forget a dose, participants will be asked to take it when they remember, and then take the next dose as usual, but if they do not remember until their next dose, to not take extra capsules to make up the missed dose.

For premenopausal subjects, they will be instructed to begin their study medication course while menstruating or after a negative beta-HCG or serum pregnancy test as below. For premenopausal subjects who do not have regular menstrual periods or are between periods, a beta-HCG level will be performed to confirm that the patient is not pregnant before starting study medication. Participants will be warned that they should avoid pregnancy while taking study medication and for two months after discontinuation. If they are sexually active, they will be advised to use barrier or nonhormonal contraceptive measures while on study.

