**Subjective safety and tolerability measures:**

**Treatment adherence.** Compliance will be measured by pill counts performed every 3 months. The number of pills taken out of the total prescribed in a 3-month period will be modeled as a random effects binomial regression model [105]. The binomial rates from 8 time points (month 3 to 24) will be modeled as unstructured mean model with 7 indicator variables as well as polynomial models over time. The random-intercept and the random intercept and slope models will be considered. The significance of the time indicators or parameters by treatment interaction will be evaluated for treatment difference in compliance.

Voluntary withdrawals will be examined at the end of the study by comparing the percent of withdrawals between the treatment groups using a chi-square test or Fisher's exact test.

**Patient reported symptoms.** The outcomes will be scored as a 5-point Likert-type scale (0 to 4) in response to questions on how much the patients are bothered by certain symptoms. The questionnaire will be administered every six months, for a total of five time points. The responses will be treated as normally distributed, as ordinal or dichotomized variable, and we will apply the linear mixed effects model or GLMM methods to compare changes between treatment groups. Because of additional time points available, in addition to the unstructured mean model, we will also fit piecewise models with join point at 6 months, considering linear and curvilinear trajectories between 6m and 24m time points.

***Exploratory Aim 1: To examine the modifying effects of demographic, clinical, and molecular characteristics on both efficacy and safety markers.***

As the primary aim of this trial is to examine the main effects of low dose tamoxifen treatment on MBD, we will examine the modifying effects of demographic, clinical, and molecular characteristics as exploratory analysis. Even if time by treatment interaction (main treatment effect) is not significant, examining the modifying effects of covariates may reveal subgroups that respond differently to low dose tamoxifen. A three-way interaction of time by treatment by modifying variable will be included in the longitudinal model containing a two-way time by treatment group interaction. Modifying effects will be considered statistically significant if the three-way interaction is significant. The covariates of interest are described below.

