**Adverse events:** We assume the rate of grade 2-4 toxicities in the placebo group to be low, at 0.5%. At the end of the study, with 94 women in each arm (accounting for 10% attrition per year), the study will have at least 80% power to detect an adverse event rate of 9.1% in the low dose tamoxifen group based on Fisher’s exact test and Type I error=0.05.

**Adherence to therapy:** We will examine the difference in adherence rates of the treatment groups by comparing the percent of pills taken across 8 time points. With 115 women at baseline per arm, assuming a constant adherence rate of 90% in the placebo group and a between-measurement correlation of 0.6 and 2-sided alternative, there will be 80% power to detect an adherence rate of about 77% in the low dose tamoxifen group.

**Voluntary withdrawals:** If the proportion of patients in the placebo arm who withdraws voluntarily by the end of the study is 10%, then with 115 women in each arm at baseline, assuming type I error=0.05, the study will have 80% power to detect a significant difference in the voluntary withdrawal rate in the low dose tamoxifen group if the withdrawal rate in the intervention group is about 28%.

**Safety biomarkers:** We focus here on total cholesterol (TC), anti-thrombin-III (AT-III), bone-specific alkaline phosphatase (BSAP), and urine N-telopeptide crosslinks (NTX). With the proposed sample sizes, the detectable effect size (described earlier) is 0.34. A relatively small % change in mean levels is detectable for TC and AT-III but larger % changes are needed to detect a significant treatment difference at t2 for BSAP and NTX.

Outcome	Assumed levels at t0 for Placebo and Low dose Tamoxifen groups	Detectable levels at t2 (80% power) for Low dose Tamoxifen group	
	Mean ± SD	Mean	Relative % change (from t0)

TC* (mg/dL)	199 ± 45	214.3	8% ↑
AT-III** (%)	100 ± 13.3	95.5	5% ↓
BSAP  (µg/L)	7.7 ± 4.5	6.2	20% ↓
NTX  (nM BCE/mM)	24.4 ± 16.1	18.9	23% ↓

\* Mean obtained from [111], sd obtained from [112]

\*\* per ARUP reference laboratory

Thus, we expect to be able to detect a 5-23% difference in the objective safety biomarkers proposed as secondary endpoints.

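### The voluntary-withdrawal power statement does not reproduce: 10% v 28% at 115 per arm has about 93-95% power, and 80% power is reached at about 24-25%

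*Combined protocol and SAP*

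**What the plan says.** Section 12.5 (Power and sample size, Aim 2, voluntary withdrawals) sets out one scenario:

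- Placebo rate: "If the proportion of patients in the placebo arm who withdraws voluntarily by the end of the study is 10"%.
- Sample size and error rate: "with 115 women in each arm at baseline, assuming type I error=0.05".
- Claim: "the study will have 80% power to detect a significant difference in the voluntary withdrawal rate" in the low-dose tamoxifen group, provided the "withdrawal rate in the intervention group is about 28"%.

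The analysis is in Section 12.4, under the subjective safety and tolerability measures. Withdrawals are examined at the end of the study by "comparing the percent of withdrawals between the treatment groups using a chi-square test or Fisher's exact test". Section 7.1 gives the allocation as 1:1. Neither section says whether this test is one-sided or two-sided.

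**The concern.** A gap of 18 percentage points from a base rate of 10% is large for 115 per arm, and one would expect power well above 80%. All the inputs are printed in the plan, so the claim can be checked without outside information.

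Safety and tolerability form Objective 1.2, and better tolerability is much of the argument for the 5 mg dose. Voluntary withdrawal is one of the tolerability outcomes. Readers use a detectable-difference statement to judge what a non-significant result rules out. Someone relying on this one would infer that a tamoxifen-arm rate of, say, 25% falls short of 80% power, when the design has about 80% power or slightly more there. The plan does not say this outright; it is the natural reading of an 80% threshold placed at 28%.

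**Working it through.** **Inputs.** Placebo rate p₁ = 0.10, tamoxifen rate p₂ = 0.28, n = 115 per arm, α = 0.05 (all Section 12.5); chi-square or Fisher's exact test (Section 12.4); 1:1 allocation (Section 7.1). Two-sided testing is assumed.

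**Trying to reproduce the stated 80%, by the pooled normal approximation to the chi-square test.**

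Power = Φ{ [ |p₂ − p₁| − 1.96·√(2p̄(1−p̄)/n) ] / √([p₁(1−p₁) + p₂(1−p₂)]/n) }, with p̄ = (0.10 + 0.28)/2 = 0.19.

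- Null standard error: √(2 × 0.19 × 0.81/115) = √(0.3078/115) = 0.0517; times 1.96 = 0.1014.
- Alternative standard error: √((0.0900 + 0.2016)/115) = √(0.2916/115) = 0.0504.
- z = (0.18 − 0.1014)/0.0504 = 1.56, so power = 94.1%.

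The stated 80% is not reproduced.

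**Other methods.** The Fisher, Pearson and Yates rows come from summing the exact binomial probabilities of every outcome that the test rejects. All rows are two-sided at 0.05.

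| Method | Power, 10% v 28%, 115 per arm | Tamoxifen-arm rate for 80% power, 115 per arm |
|---|---|---|
| Pearson chi-square, exact enumeration | 94.7% | 23.6% |
| Fisher's exact, exact enumeration | 92.8% | 24.5% |
| Pooled normal | 94.1% | 23.8% |
| Arcsine | 94.7% | not solved |
| Yates chi-square, exact enumeration | 92.5% | not solved |
| Continuity-corrected normal | 91.8% | 24.8% |

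Exact power either side of the 80% point, at 115 per arm:

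- 10% v 24%: 77.6% (Fisher), 82.1% (chi-square).
- 10% v 24.5%: 80.2% (Fisher), 84.4% (chi-square).

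**The same question as a sample size.** For 80% power at 10% v 28%:

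n = (1.96·√0.3078 + 0.8416·√0.2916)² / 0.18² = (1.0874 + 0.4545)² / 0.0324 = 73.4.

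This rounds up to 74 per arm, or 85 with continuity correction. The plan has 115.

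**Could another reading give 80%?**

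- *Reduced n.* The adverse-event statement in Section 12.5 works "with 94 women in each arm (accounting for 10% attrition per year"). At 94 per arm, 10% v 28% has 86.4% (Fisher), 88.8% (pooled normal) or 89.8% (chi-square) power. The most conservative formula, with continuity correction, gives 84.8%. Power of 80% is reached between 25.3% (chi-square) and 26.8% (continuity-corrected), with Fisher at 26.4%.
- *One-sided test.* By the pooled normal formula, power at 115 per arm rises to 97.0%, further from 80%.
- *Stricter α.* α = 0.01 would give 82.3% at 115 per arm, but the sentence specifies 0.05.

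**The case against.** The best case for the plan is that a smaller, unstated denominator was used. The neighbouring adverse-event calculation cuts 115 to 94 for attrition, and at 94 per arm Fisher's test reaches 80% power at 26.4%, within about 1.6 points of a figure the plan gives only as approximate. This does not hold up. The sentence states 115 at baseline, and withdrawal is itself the outcome, so women who withdraw belong in the denominator. Even at 94 per arm the power at 28% is 86-90% under the two named tests.

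Three other points stand, but they limit the weight of the finding rather than the finding itself:

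- The error is conservative: the trial has more power for this comparison than it claims.
- Nothing else depends on the figure. The 230 women come from the mammographic-density calculation, and the withdrawal test will be run on observed counts whatever the planning statement says.
- The plan allows two tests that differ slightly. At 24% Fisher's test falls just short of 80% (77.6%), so a replacement figure should say which test it refers to.

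**Conclusion.** The concern holds. On the plan's own inputs, power at 10% v 28% is about 93% (Fisher) to 95% (chi-square), not 80%. The rate detectable with 80% power is about 23.6% (chi-square) to 24.5% (Fisher), an absolute difference of roughly 14 percentage points rather than 18.

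This rests on one assumption, two-sided testing, and a one-sided test would widen the discrepancy. None of the methods tried at α = 0.05, at either 115 or 94 per arm, gives 80% power at 28%. The importance is minor: one misstated planning figure for a secondary tolerability comparison, in the conservative direction.

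**What to change.** Correct the sentence in Section 12.5 in one of two ways:

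- keep 80% power and give the tamoxifen-arm withdrawal rate as about 24% for the chi-square test or about 24.5% for Fisher's exact test; or
- keep 28% and state the power as about 93% (Fisher) or 95% (chi-square).

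In either case, state that the test is two-sided (if that is the intention), name the test the figure refers to, and say that all 115 randomised women per arm form the denominator. The cost is one figure and a few words, with no change to the design, sample size or analysis.

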***Exploratory Aim 1: To examine the modifying effects of demographic, clinical, and molecular characteristics on MBD.***

These analyses will be considered exploratory. We anticipate relatively low power as interaction effects are typically smaller and have relatively larger standard errors than main effects. Examining interactions is similar to comparing treatment effects among smaller sub-samples, thus power is reduced. An example is comparing the treatment effects of low dose tamoxifen between women who are pre- and post-menopausal at the time of study enrollment. Power estimates for this example were obtained by simulation. First, we estimated the linear mixed effects models of RTMBD for the 16 pre- and 25 post-menopausal control women in the Puget Sound NSABP P-1 data [106]. Based on our power calculation which showed that a 20% reduction in MBD is detectable at year 2 at 80% power with 100 women per arm without attrition, linear mixed effects models for the pre- and post-menopausal groups in the treatment arm were set up that included the treatment by time coefficient  $\beta=0.2338$  corresponding to the detectable effect size. We also included another treatment by time parameter  $\Delta$  to allow differential treatment effect by menopausal status ( $+\Delta/2$  in pre-menopausal women and  $-\Delta/2$  in post-menopausal women), i.e. an assumption of larger treatment effect in pre- than in post-menopausal women). Random sets of RTMBD at (t0, t1, t2) were generated from the corresponding trivariate normal distributions for the four groups (67 pre- and 33 post-menopausal women in each treatment arm). Menopause-specific covariance matrices (assuming compound symmetry) estimated from the Puget Sound NSABP P-1 data were used. Power for detecting a significant  $\Delta$  under the alternative hypothesis of 100%, 75%, and 50% of the main treatment effects ( $\beta=0.2338$ ) was estimated from 1000 random samples of the trial data by fitting the linear mixed effects model (linear in time) that included the treatment by time by menopausal status term. The model also included menopause status main effects and menopause by time interactions. Since interactions are expected to be smaller than main effects,  $\Delta=0.2338$  is likely an overestimate of the interaction effects. Even with this overestimation, the anticipated power is only 40% (corresponds to treatment-related reduction in MBD of 28% relative to placebo at year 2 in the pre-menopausal group versus 13% reduction in the post-menopausal group). For the 75% and 50% alternative for  $\Delta$ , power is even lower (24% and 12%, respectively). Thus, power for examining other modifying effects are anticipated to be similarly low or lower.

***Exploratory Aim 2: To examine the relationship between a low-dose tamoxifen regimen and clinical measures of efficacy and toxicity.***

This aim will also be considered exploratory as the study was not powered to detect treatment difference in these adverse outcomes. As the events of interest have very low incidence rates in both treatment groups (see Table 3 of Investigational Brochure), the study will not have any power (<5%) to detect the relative risks seen in NSABP P-1 Trial. The power for detecting treatment differences in the proportion of women anticipated to experience hot flashes and gynecological symptoms is somewhat better, 90% for vaginal discharge (prevalence rates of 35% in placebo and 55% in treatment groups), but only

41% for hot flashes (prevalence rates of 68% in placebo and 80% in treated groups), and 5% for vaginal bleeding (22% versus 23%).

## 13.0 REGISTRATION GUIDELINES

Patients will be registered using an online secure website developed by Sharp Clinical Services (IWRS). To register a subject, the CRN or CRA must complete the intake form and eligibility worksheet online. This process is fully described in the [Screening and Enrollment SOP](#). After verification of eligibility by the coordinating center, randomization will be performed and treatment assigned using the Sharp Clinical Services IWRS. This procedure is fully described above in Section 12.3.

### 13.1 Procedures for On-Study and Treatment Deviations

Protocol waivers and/or treatment deviations are generally not allowed. However, should the need arise to amend the protocol in order for the protocol document to more accurately reflect the initial intent of the investigator(s), then the treating physician must contact the PI obtain approval. If approved, the protocol PI must immediately submit an amendment to the protocol. A backup for the originating PI has been designated and is specified in the registration worksheet.

## 14.0 RECORDS TO BE KEPT AND DATA SUBMISSION SCHEDULE

### 14.1 Confidentiality of Records

All research records will be stored in locked file cabinets at each site. Computer files with coded subject information will have restricted access passwords available only to the local PMT.

### 14.2 Subject Consent Form

The original signed [Consent Form](#) will be placed in the medical record. A copy will be given to the subject and a copy will be filed in the research record.

### 14.3 Data Collection Forms and Submission Schedule

Specific patient-administered forms to be used and the timing that they will be submitted are outlined in Section 9.0. In addition, the CRA/CRN will be responsible for completing the forms below and entering the information into the study EDC website.

#### Screening and Baseline Forms:

The CRA/CRN will fill out the [Intake Form](#) at the time of the prescreen interview, and the [Eligibility Worksheet](#) at the time of the patient's screening visit for study enrollment. These forms and associated documentation must be fully submitted *within 14 days* of the prescreening interview and screening visit, respectively. Should the patient be registered as a participant, the CRA/CRN will complete the baseline [Primary Cancer Treatment History Form](#), the [General History and Physical Form](#), and the [Clinical Breast Exam Form](#). These should be submitted *within 28 days* of the baseline visit. Please refer to the [Screening and Enrollment SOP](#) for submission instructions.

#### Breast Imaging and Specimen Submission Forms:

The CRA/CRN will complete the **Breast Imaging Submission Form** to accompany submission of the baseline and annual screening mammograms and, if applicable, annual breast MRIs. Scheduling of these imaging tests are outlined in Section 9.1. RPFNA-protein, RPFNA-Cytology, and **Blood and Urine Specimen Submission Forms** will be completed to accompany submission of RPFNA tissue and blood specimens as outlined in Sections 11.2.3 (tissue) and 11.3.1–11.3.3 (blood).

#### Breast Event Form:

The NSABP developed a data capture form to record breast events, which they used in the NSABP P-1 and P-2 breast cancer prevention trials. This form has been adapted for use in this study. The CRA/CRN will complete the **Breast Event Form** should a subject receive a diagnostic breast biopsy while on study, or during follow-up. Should such a biopsy reveal DCIS or invasive breast cancer, the subject will be withdrawn from the study treatment as outlined in Section 6.3. For other breast events, the subject may continue on the trial.

#### Other Event Form:

The NSABP developed a data capture form to record other cancer and other potentially protocol-related medical events, which they used in the NSABP P-1 and P-2 breast cancer prevention trials. This form has been adapted for use in this study. The CRA/CRN will fill out the **Other Event Form** should a subject receive a cancer diagnosis other than breast cancer or require inpatient or outpatient procedure that could be potentially related to protocol while on trial or during follow-up. Only for specific events outlined in Section 6.3 will the subject necessitate withdrawal from the study. Otherwise, the subject may continue on the trial.

#### Treatment Interruptions:

The CRA/CRN will fill out a **Treatment Withholding Form** should a subject report an interruption for any reason while on trial. The patient-reported reason and both hold and restart dates will be recorded. If the subject voluntarily chooses to withdraw from study, then a **Study End Form** will be used instead. However, if the subject chooses to continue on trial, then the **Treatment Withholding Form** will be submitted. If a patient is off study medication for more than 90 consecutive days, then they must be withdrawn from the study. In that case, the CRA/CRN will submit both **Treatment Withholding** and **Study End Forms**.

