### 6.3 Criteria for Discontinuation of Study Protocol Therapy

- Patient requests to withdraw from study
- Treatment interruption longer than 90 consecutive days
- A breast or gynecologic event (see definitions below)
- Pregnancy
- The occurrence of a grade 2 toxicity with *probable* or greater attribution without resolution within 72 hours, or any grade 3 or 4 toxicity with *possible* or greater attribution meeting definitions below
- Death

A *breast event* is defined as a new diagnosis of DCIS or invasive BC. These events are expected to occur as a consequence of the high risk study population. In the case that it should occur, the subject will be taken off study and referred to the appropriate breast surgeons and medical oncologists for proper diagnostic work-up and treatment. For subjects who develop atypical hyperplasia (AH) or lobular carcinoma in-situ (LCIS), or any other form of benign breast disease, their specific histologic diagnosis and the date of diagnosis will be recorded, but they may continue on study.

A *gynecologic event* is defined as a new diagnosis of endometrial carcinoma or uterine sarcoma. Although these events may occur sporadically, they have been associated with standard dose tamoxifen and therefore are listed among criteria for discontinuation of study treatment. In the case that a subject should experience dysfunctional uterine

bleeding of any etiology, the subject will be referred to a gynecologist for proper diagnostic work-up. Should such a work-up lead to a diagnosis of endometrial carcinoma or uterine sarcoma, the subject will be taken off study and referred to a gynecologic oncologist for appropriate treatment. Otherwise, their specific histologic diagnosis and the date of diagnosis will be recorded, but they may continue on study.

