Participants must not be planning to become pregnant for two years to be eligible for the study, and they will be warned about the importance of not becoming pregnant while on study at the time of enrollment. They will be advised to use either a barrier method or another nonhormonal form of contraception (eg. hormone-free IUD) for all sexual activity during the course of the study. Nevertheless, occurrence of an unplanned intrauterine pregnancy while on study will be an indication for immediately stopping treatment and the patient must withdraw from the study. If the patient should become pregnant while on study, or within two months after discontinuing therapy, her treatment assignment will be unblinded immediately. If the patient was randomized to tamoxifen, then they must be apprised of the potential risk of spontaneous abortion, birth defects, or a DES-like syndrome.

The Principal Investigator (PI) at each site is responsible for monitoring protocol conduct and reporting to their Institutional Review Board (IRB) any adverse events (AEs) related to either the study medication per their institutional guidelines. AEs must also be reported to the Coordinating Center (UAB) per instructions in Section 8.0. The NCI common toxicity criteria for adverse events Version 4.0 (CTCAE v.4.0, Publish Date 10/19/2009) will be used to assess toxicity.

With the exception of vasomotor and gynecologic symptoms commonly associated with menopause, all grade 2 or greater toxicities of clinical significance with *possible* or greater attribution (please refer to Section 8.3 for definition) to the study drug will be reviewed by the Protocol Management Team (PMT) at the local site. The PMT includes the consortium PI, the consortium co-investigator, and the CRA/CRN.

- Any grade 2 toxicity besides vasomotor and/or gynecologic symptoms commonly associated with menopause with *probable* or greater attribution to the study drug will be brought to the attention of the local PI (within 24 hours of knowledge of the event) for close monitoring. If the symptom resolves or improves within 72 hours, the patient may continue on the study medication. Otherwise, the patient will be unblinded and taken off therapy.
- A patient reporting grade 3-4 toxicity with *possible* or greater attribution to the study drug will be unblinded and taken off protocol therapy.

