### 7.3 **Criteria for Removal from Treatment**

7.3.1 Treatment will be discontinued if a subject experiences an adverse event which the investigator deems related to the study medication or which will interfere with the ability of the subject to comply with the protocol. See section 6.3 for specific rules.

7.3.2 A subject may always voluntarily withdraw from treatment whenever she wishes.

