#### Study End Form:

The CRA/CRN will fill out the **Study End Form** at the time the subject goes off trial, even if they complete the full treatment course. This form records whether or not the subject completed the trial per protocol, voluntarily withdrew, or was withdrawn for another reason. For voluntary withdrawals, subjects will be asked to clarify if it was due to intolerable side effects of treatment or if it was due to another reason.

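### Sections 6.3 and 14.3 disagree on whether stopping study drug means leaving the study, and no section says whether density is collected afterwards for the intention-to-treat analysis

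*Combined protocol and SAP*

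**What the plan says.** **Interruption over 90 days.** Section 6.3, whose title concerns discontinuation of protocol therapy, lists "Treatment interruption longer than 90 consecutive days". Section 14.3 (Treatment Interruptions) says of the same event: "If a patient is off study medication for more than 90 consecutive days, then they must be withdrawn from the study", and asks for a Study End Form. That form is completed "at the time the subject goes off trial, even if they complete the full treatment course".

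**New DCIS or invasive breast cancer.** Section 6.3: "the subject will be taken off study and referred to the appropriate breast surgeons and medical oncologists". Section 14.3 (Breast Event Form): "the subject will be withdrawn from the study treatment as outlined in Section 6.3". Section 14.3 (Other Event Form) in turn describes events listed in 6.3 as ones that require withdrawal from the study.

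**After withdrawal.** Sections 9.5 and 14.3 provide an Annual Follow-Up Form and event forms for medical events, including in women who withdrew early. Neither mentions density.

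**Density and its analysis.** Section 11.1 times mammograms at one and two years from treatment initiation, with no condition that the woman is still on drug. Section 10.0 says the biological response of all eligible subjects will be reported. The study calendar calls annual mammograms standard of care. Section 12.4 plans an intention-to-treat linear mixed model including everyone with baseline density. It notes that the model is valid if data are missing at random, and adds pattern-mixture models, a dropout-propensity covariate and an adherence-based as-treated analysis.

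**The concern.** An intention-to-treat comparison of density at year 2 needs year 2 density from women who stopped drug, or a stated assumption that stands in for it. If a site reads 14.3 literally, a woman off drug for more than 90 days leaves the study and her later films may not be sent. A site that reads 6.3 literally may keep sending them. Two sites could therefore treat the same woman differently.

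Where the films are not sent, the mixed model fills the gap from women in the same arm who are still observed, most of them on drug. If density partly returns after stopping, the reported effect is larger than the effect in all women as randomised, and the planned sensitivity analyses may agree with it for the wrong reason.

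**Working it through.** **1. The plan's own figures.** Section 12.5 gives an effect size of 0.25 SD at t2, correlation 0.8, two-sided alpha 0.05, 100 per arm for 80% power, and 115 per arm with 10% attrition at each annual visit.

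- SD of change = sqrt(2 × (1 − 0.8)) = 0.632, so SE = sqrt(2 × 0.4/n). At n = 100, SE = 0.0894 and 0.25/0.0894 − 1.96 = 0.835, giving power 79.8%. The n for 80% is 100.5. The plan's 100 is reproduced.
- With year 2 retention 0.9 × 0.9 = 0.81, the variance of the t2 − t0 contrast is 2 × (1 + 1/0.81 − 1.6/0.9)/n = 0.9136/n. At n = 115, SE = 0.0891 and power is 80%. The plan's 115 is reproduced. A likelihood calculation on the dropout patterns gives 78.5% at 115, which is close.
- Square-root scale: sqrt(18.72) − sqrt(14.89) = 0.468, which matches 2 × 0.2338, with 0.2338 taken from Exploratory Aim 1 in 12.5.

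**2. Size of the lean.** Let f be the share who stop drug and k the share of the effect they keep at t2. Neither is in the documents, so both are assumptions. The effect as randomised is 0.25 × m, with m = 1 − f(1 − k).

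Some late stoppers would still supply a Day 730 film. The calendar window of ±60 business days is 84 calendar days, so the film can fall from Day 646 to Day 814. With the film at Day 646, a woman who stops after Day 646 − 90 = 556 is still on study. If stopping times are uniform (assumed), the share of stoppers still observed is L = (730 − 556)/730 = 23.8% at most.

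Ratio of observed effect to effect as randomised = {1 − [Lf/(1 − (1 − L)f)](1 − k)}/m.

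Worked case, f = 0.19, k = 0: m = 0.81.
- L = 0: 1/0.81 = 1.235.
- L = 0.238: Lf = 0.0452 and 1 − 0.762 × 0.19 = 0.855, so (1 − 0.0529)/0.81 = 1.169.

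Overstatement (range from L = 23.8% to L = 0):

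| Share stopped | None kept | Half kept | All kept |
|---|---|---|---|
| 5% | 4-5% | 2-3% | 0% |
| 10% | 8-11% | 4-5% | 0% |
| 19% (all planned attrition) | 17-23% | 8-10.5% | 0% |

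Back on the density scale with 19% stopped, the planned 20.5% relative reduction becomes 1 − (4.327 − 0.81 × 0.468)²/18.72 = 16.8% with none kept, and 18.6% with half kept.

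Attrition also includes withdrawn consent and loss to follow-up, which no rewording of 14.3 would recover. If half of the missing women could be retrieved, the worst case falls from 17-23% to about 8-10.5%.

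**3. Do the planned checks detect it?** Large-sample simulations used correlation 0.8 and no film after stopping.

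- *Propensity covariate* (18.5% stopped, none kept): true effect 0.206 SD; mixed model 0.253; mixed model with propensity 0.253. The propensity is built from baseline covariates only, so the analysis still assumes missing at random.
- *Pattern-mixture average* (10% stopping per year, none kept): true 0.202 SD. With a complete-case restriction the average is 0.250. With linear extrapolation for the t0-t1 pattern and the completers' effect for the t0-only pattern it is also 0.250.

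The linear-in-time model in 12.4 could supply a t2 value for women with t0 and t1. For women with t0 only, the plan states no restriction, and the average cannot be computed without one.

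**The case against.** **Some of the apparent contradictions are not contradictions.** A reader might add that 6.3 takes a pregnant woman out ("will be an indication for immediately stopping treatment and the patient must withdraw from the study") but removes a woman with grade 3-4 toxicity only from therapy ("to the study drug will be unblinded and taken off protocol therapy"). These are different events and may have different rules. Likewise the 6.3 entry on a patient asking to leave the study and 7.3 ("A subject may always voluntarily withdraw from treatment whenever she wishes") can be two separate options. Neither pair supports the point. The 90-day rules could even both hold, with therapy ending and the woman also leaving. The Breast Event Form text defers to 6.3, and the Other Event Form text suggests the authors use off therapy and off study loosely. That reading stands as far as it goes, but it makes the missing density matter more, because then every such woman leaves the study.

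**The gap is silence, not a prohibition.** A reader might infer that the plan excludes density after withdrawal. It does not: Sections 10.0 and 11.1 leave room for it, and a follow-up SOP that is not part of these documents may cover it. The 90-day sentence also sits in a paragraph about hold and restart dates, so its application to permanent stopping is a reading, though its words cover it. What remains is that a stated rule removes women and no stated rule keeps their films.

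**The plan foresees non-ignorable dropout.** Section 12.4 says so, collects reasons and plans sensitivity analyses. This softens the point. It does not answer it, for the reasons in step 3, and the as-treated analysis supplies no missing films.

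**Conclusion.** The point holds in limited form. Sections 6.3 and 14.3 need consistent wording, and the plan must say whether density is collected and analysed after drug is stopped. Until it does, the intention-to-treat label in 12.4 may describe an estimate that leans towards the on-drug effect.

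The size is unknown from the documents. It rests on three assumptions: sites stop sending films after withdrawal, the density effect fades after stopping, and a given share of women stop. With full persistence there is no bias. With 5-10% stopping and half the effect kept, it is about 2-5%. The 17-23% figure is a worst case and should not be read as the expected bias: it takes all 19% attrition as drug stopping with nothing kept, and the documents support neither. Nor do they support a claim that the sample size is wrong, since both of the plan's figures reproduce.

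**What to change.** 1. Reconcile Section 6.3 with the Treatment Interruptions, Breast Event Form and Other Event Form paragraphs of 14.3, so that stopping drug is recorded separately from leaving the study. No drug-stopping rule needs to change.
2. Unless consent is withdrawn, collect the standard-of-care mammograms nearest Day 365 and Day 730 after drug stopping. Flag those that miss the imaging specifications in 9.1 and 11.1.1, and analyse them by randomised arm. Say in advance how densities after pregnancy or breast cancer treatment are handled. Alternatively, state that the target is the on-drug effect and drop the intention-to-treat label.
3. State the pattern-mixture restriction, at least for the t0-only pattern. A reference-based or delta-adjusted sensitivity analysis is optional; the reference-based result would be too low if the effect persists.

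**Cost.** A short amendment, SAP wording and image retrieval work. Some routine films will miss the raw-format, large-paddle, same-machine or cycle-timing requirements. The effect as randomised may be smaller. By the formula in step 1, with 19% stopped and 115 per arm fully observed, power is about 68%, 77% or 85% with none, half or all of the effect kept. If half of these women are retrieved (about 104 per arm) it is about 72%, 77% or 81%. Without retrieval the same formula gives about 77% for the on-drug effect (93 per arm).
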